8. ASSESSMENT OF SAFETY

The safety endpoints of this investigation will be:

- Incidence of local and systemic adverse events;
- Changes from baseline in vital signs (blood pressure and heart rate).

Methods of assessment

Adverse events

Definitions, coding, methods of collection of adverse events and medical device incidents are described in details in Section 9.

Vital signs

Vital signs will be recorded at each investigation visit.

Systolic and diastolic blood pressure will be measured in sitting position after at least 5 minutes rest. Heart rate will be measured for one minute just prior to the sitting blood pressure measurement.

9. ADVERSE EVENTS

9.1 Definitions

An Adverse Event (AE) is defined as "any untoward medical occurrence, unintended disease or injury, or untoward clinical signs (including abnormal laboratory findings) in subjects, users or other persons, whether or not related to the investigational medical device".

An **Adverse Device Effect (ADE)** is defined as an AE related to the use of the medical device and includes any AEs resulting from insufficient or inadequate instructions for use, deployment, implantation, installation or operation, or any malfunction of the medical device. It also includes any AE resulting from user error or from intentional misuse of the medical device.

NOTE

in this study local pain/burning at the site of injection occurred during the admnistration and /or during the 3 hours following the procedure

WILL BE NOT JUDGET AS AE/ADE

Device deficiencies (DDs) are defined as any inadequacy of a medical device with respect to its identity, quality, durability, reliability safety or performance, including malfunctions, use errors, and inadequate labelling. A malfunction is defined as failure of an investigational medical device to perform in accordance with its intended purpose when used in accordance with the instructions for use or protocol. All device deficiencies will be documented during the clinical investigation and reported to the Sponsor on the appropriate form. A device deficiency that did not lead to an adverse event but could have led to a medical occurrence if suitable action had not been taken, if intervention had not been made, or if circumstances had been less fortunate, must be reported in the same way as an adverse event.

A Serious adverse event (SAE) is defined as an AE that:

- a) Leads to death
- b) Leads to serious deterioration in the health of the subject that results in
 - 1) A life-threatening illness or injury, or
 - 2) A permanent impairment of a body structure or a body function, or
 - 3) In-subject or prolonged hospitalisation, or
 - 4) Medical or surgical intervention to prevent life-threatening illness or injury or permanent impairment to a body structure or a body function

c) Leads to foetal distress, foetal death or a congenital abnormality or birth defect.

Planned hospitalization for a pre-existing condition, or a procedure required by the CIP, without serious deterioration in health, is not considered a SAE.

A Serious adverse device effect (SADE) is defined as any ADE that results in any of the consequences characteristic of a serious adverse event (SAE).

An **Unanticipated serious adverse device effect (USADE)** is defined as a SADE which by its nature, incidence, severity or outcome is not identified in the current version of the risk analysis report.

An Anticipated serious adverse device effect (ASADE) is an effect which by its nature, incidence, severity or outcome has been identified in the current version of the risk analysis report.

According to MEDDEV 2.12-1, Rev. 8, a **medical device incident** is defined as 'any malfunction or deterioration in the characteristics and/or clinical performance of a device, as well as any

inadequacy in the labelling or the instructions for use, which, directly or indirectly, might lead to or might have led to the death of a subject, or USER or of other persons or to a serious deterioration in their state of health'. A medical device incident that would require reporting includes:

- a) Serious public health threat: Any event type which results in imminent risk of death, serious deterioration in state of health, or serious illness that requires prompt remedial action (MEDDEV 2.12-1 rev.8).
- b) Death or UNANTICIPATED serious deterioration in state of health of a subject that results in:
 - 1) A life-threatening illness or injury, or
 - 2) A permanent impairment of a body structure or a body function, or
 - 3) In-subject or prolonged hospitalization, or
 - 4) Medical or surgical intervention to prevent life-threatening illness or injury or permanent impairment to a body structure or a body function
- c) Other events: events that have an established link between the device and the event

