1.4 Potential risks and benefits

Risks associated with hyaluronic acid

Hyaluronic acid containing fillers are generally well tolerated. The most common adverse events are local pain, brusing, ecchimosys, erythema and bleeding - generally mild and transient. Serious adverse events are rare. Early adverse reactions to hyaluronic acid fillers include vascular infarction and compromise; inflammatory reactions; injection-related events; and inappropriate placement of filler material. Among late reactions are nodules, granulomas, and skin discoloration. Most adverse events can be avoided with proper planning and technique. Detailed understanding of facial anatomy, proper patient and product selection, and appropriate technique can further reduce the risks⁴².

Risks associated with lidocaine

Large data on lidocaine toxicity are available on database as TOXNET, MEDLINE, RTECS (Register of toxic effects of chemical substances). The incidence of side effects is directly proportional to the total dose of local anaesthetic agent injected; low doses are generally well tolerated. The initial symptoms of anaesthetic induced toxicity include light-headedness, circumoral numbness, diplopia, and tinnitus. These effects are generally mild and short-lasting. Serious events include slurred speech, tremors, seizure and respiratory depression.

There are no expected serious risks or complications that may emerge from the administration of the two investigational medical devices (HA and HA+lidocaine) according to treatment schedule defined in this investigational protocol. Therefore, it is expected that benefits from the participation in this investigation will outweigh the theoretical risks.

⁴² Signorini M, Liew S, Sundaram H et al. *Global Aesthetics Consensus: Avoidance and Management of Complications from Hyaluronic Acid Fillers—Evidence- and Opinion-Based Review and Consensus Recommendations*. Plast Reconstr Surg. 2016; 137(6): 961–971.

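### The NOTE in section 9.1 excludes early injection-site pain from AE/ADE, and so from SAE/SADE, with no exception for seriousness or treatment and no rule for pain that outlasts 3 hours

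*Combined protocol and SAP*

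**What the plan says.** Section 9.1 gives broad definitions of AE and ADE and then adds a NOTE. It describes certain pain, "in this study local pain/burning at the site of injection occurred during the admnistration and /or during the 3 hours following the procedure", and rules that it "WILL BE NOT JUDGET AS AE/ADE".

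The serious classes in the same section are built on those two terms. It states: "A Serious adverse event (SAE) is defined as an AE that" meets one of the listed outcomes. A SADE is likewise an ADE with such an outcome, and a USADE is nested one level further: it "is defined as a SADE which by its nature, incidence, severity or outcome is not identified in the current version of the risk analysis report".

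Two other classes are defined without reference to AE or ADE: device deficiencies and medical device incidents. An incident is "any malfunction or deterioration in the characteristics and/or clinical performance of a device, as well as any" inadequacy in labelling or instructions that could lead to death or serious harm. Section 9.3 gives both classes their own reporting duty.

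Section 2.2 makes the comparison of HAL and HA on safety a secondary objective. Section 8 names the incidence of local and systemic AEs as a safety endpoint. Section 10.2.5 compares the incidence of treatment-emergent AEs by McNemar test.

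**The concern.** Keeping ordinary procedural pain out of the AE listing is sensible here, because pain is the primary endpoint and has its own VAS record. The difficulty is that the NOTE is wider than that purpose. It looks only at where and when the pain occurred, not at whether it was serious, needed treatment or went away.

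Two things are at stake. The first is individual reporting: in-window pain cannot formally become an SAE or SADE, however it turns out. The second is the comparison of the devices. Section 1.4 puts local pain first among the common adverse events of these fillers, and the two devices differ by an anaesthetic whose effect section 1.2 describes as declining over the first hour. Later or persistent pain is therefore a plausible place for the sides to differ, in either direction, and it may be missing from the treatment-emergent tables. In an investigation done before CE marking, that is worth closing.

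**Working it through.** The plan gives no figure on this point, and the power calculation in 10.2.1 does not bear on it. The check is a reading of the definitions in sequence.

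1. **Conditions in the NOTE.** Symptom (pain or burning), place (injection site) and time (administration or the next 3 hours). It has no condition on seriousness, intensity, treatment or resolution, and none is supplied elsewhere in the protocol.

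2. **Nesting.** SAE is a subset of AE, SADE of ADE, and USADE of SADE. An event that is neither AE nor ADE is in none of them.

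3. **What runs on AEs.** The recording duty in 9.2 covers AEs and device deficiencies. Its extension to every classification applies only to what already qualifies. The tables, related-event counts and McNemar test in 10.2.5 use AEs only.

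4. **What else could hold the information.** The VAS ends at 60 minutes (sections 6.1 and 7), which leaves 180 − 60 = 120 minutes of the exempt window unmeasured. That gap is a separate matter: a VAS running for the full 3 hours would still not classify serious, treated or persistent pain. The next scheduled visit is at week 2. A drug given for pain would appear as a concomitant medication (5.5), which is not a safety report. The deficiency and incident routes are independent of AE status.

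Applied to the possible cases:

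| Event | Status as written |
|---|---|
| In-window pain, mild, untreated, gone by 3 hours | Not an AE; a reasonable exemption |
| In-window pain that needs treatment | Not an AE; seen only as a concomitant medication |
| In-window pain alone that meets a seriousness outcome, such as hospitalisation | Not an AE, so not an SAE or SADE; only the deficiency or incident route is left |
| Pain that starts in the window and continues past 3 hours | No rule |
| Pain that starts after 3 hours | AE |
| Vascular compromise or inflammatory reaction, with or without pain | AE in its own right |

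5. **The fourth row.** The result depends on what *occurred* means. If it means onset, pain that begins at injection stays exempt however long it lasts. If it means presence in the window, the part after 3 hours is an AE. Section 10.2.5 uses *occurred* and *started* in parallel for AEs before and after application, and 9.4 records AEs by onset and resolution dates, which leans towards onset. Neither passage settles it.

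**The case against.** The best defence is that the NOTE covers a symptom only. Section 1.4 warns that "Early adverse reactions to hyaluronic acid fillers include vascular infarction and compromise; inflammatory reactions; injection-related events" and misplaced filler can occur early, and a reader might infer that the NOTE lets such reactions go unrecorded. It does not: each is an untoward event in its own right and stays an AE whether or not it hurts. What remains is pain noted alone, before or without a diagnosis.

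A reader might also infer that serious pain need never be reported at all. That is too strong. Incidents include "Death or UNANTICIPATED serious deterioration in state of health of a subject that results in" hospitalisation, among other outcomes, and section 9.3 sets a 24-hour duty covering device deficiencies and incidents. These routes are only partial, because an incident requires a malfunction, a deterioration in characteristics or performance, or a labelling or instruction inadequacy. Nor do they enter the treatment-emergent tables.

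Nor does the NOTE turn every treated case into a missed SAE. The intervention criterion in 9.1 concerns preventing life-threatening illness or injury or permanent impairment. Pain relieved by an analgesic would not meet it even without the NOTE. Such pain is lost as an AE, not as an SAE.

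Finally, it is tempting to say that pain lasting for days is exempt. The text does not establish that, since it rests on reading *occurred* as onset. It is equally fair to note that section 1.4 calls the common events, local pain among them, generally mild and transient, so most of what the NOTE removes is what it was meant to remove.

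These points narrow the concern. They do not supply the missing exception for seriousness and treatment, or the missing rule for persistence.

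**Conclusion.** The point holds in limited form. Read exactly, the NOTE removes in-window injection-site pain from AE/ADE, and through the nested definitions from SAE, SADE and USADE and from the treatment-emergent comparison of HAL and HA. It makes no exception for seriousness or need for treatment and gives no rule for pain that crosses the 3-hour mark, so different staff could classify the same persistent pain differently.

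The conclusion on seriousness and treatment rests on the wording alone. The conclusion on persistence rests on the text being silent, not on one reading of it. No size can be given: the documents contain no rate of serious, treated or persistent injection-site pain, and purely serious pain without another diagnosis may be rare. This is a cheap improvement to safety capture for a stated secondary objective, and it does not touch the primary analysis.

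**What to change.** Amend the NOTE in 9.1, and the matching CRF instruction, to say three things:

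- The exemption applies only to local pain or burning at the injection site that is non-serious, needs no treatment and has resolved within the 3 hours.
- All other injection-site pain is recorded as an AE with its side and true onset time. The side is needed because the devices are compared within the face, and the AE report contents listed in 9.4 do not name it.
- The NOTE does not override the SAE and SADE definitions or the reporting duty in 9.3.

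This keeps transient procedural pain with the VAS endpoint. The cost is a short change to the text and a few more AE records to code and follow.

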9.2 Procedures for Reporting and Recording Adverse Events

It is responsibility of the Investigator to collect all adverse events (both serious and non-serious) derived by spontaneous, unsolicited reports of subjects, by observation and by routine open questionings (e.g., how have you felt since I saw you last? Is there anything new that you wish to discuss?). Overall the Investigator shall record every adverse event and observed device deficiency, together with an assessment.

All Adverse Events/devices deficiency occurring during the clinical investigation must be documented in the subject's medical records and in the Adverse Event forms on the CRF, irrespectively of their classification.

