²⁶ Fagien S, Monheit G, Derek Jones D *et al. Hyaluronic acid gel with (HARRL) and without lidocaine (HAJU) for the treatment of moderate-to-severe nasolabial folds: a randomized, evaluator-blinded, phase III study.* Dermatol Surg 2017; 0, 1–8

management usually requires some form of anaesthesia to be administered before treatment. Topical formulations, percutaneous injections and nerve blocks using lidocaine are most widely used ^{22 23}. Moreover, topical anaesthesia is often insufficient at completely eliminating pain and requires an extended period of time of onset. Local anaesthesia adequately controls pain but can distort the area of treatment, making it more difficult to determine the end point of treatment²⁷. Nerve blocks are effective, but their prolonged duration of action and transient cosmetic side effects are often unsatisfactory to subjects. In some cases, nerve block procedures should be avoided as in the case of nasolabial fold correction: infraorbital nerve block injection could add volume to the NLF, hampering a correct estimate of the filler volume needed ²⁸. In addition, many doctors are unfamiliar with performing nerve blocks 29. Moreover, the separate administration of the anaesthesia can be associated with adverse events such as bruising, ecchymosis, and edema^{30 31}. Consequently, a number of physicians routinely add lidocaine solution to the available fillers in order to avoid injectable anaesthesia. Not only does this practice prompt questions of sterility, consistency, and quality of the final mixture, but it can change the product's flow characteristics and effectiveness by diluting the HA concentration with the lidocaine solution. Therefore, the ability to reduce pain by combining lidocaine with the dermal fillers represents one target for the advancement of current HA fillers. The lidocaine is added at 0.3% during the manufacturing process as a dry/powder substance and therefore does not dilute or increase the volume of the soft tissue filler ²⁸. Several studies that examined and compared HA fillers with and without lidocaine revealed significantly less pain and, in some, less erythema, swelling, and bruising with adjunct lidocaine ^{21 22 27 28 32 33 34 35}. Pre-incorporated lidocaine in collagen fillers is shown to cause less bruising and swelling after injection, which could translate to HA fillers ³⁶. Lidocaine is also shown to function as an antihistamine in lower concentrations, inhibiting its release from mast cells ³⁷. Furthermore, returning to the previously injected area for optimal results frequently causes no more pain. It appears that the reduction and/or the absence of pain during the procedure may contribute to the injection of the lidocaine version versus the lidocaine free version being perceived as easier to perform by some injectors.

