2.2 Secondary objectives

The secondary objectives of this investigation are:

- To assess and compare the safety of HAL and of HA;
- To assess and compare and the efficacy of HAL and of HA injection. Clinical efficacy will be determined by the
 - Global Aesthetic Improvement Scale (GAIS), done by the subject at weeks 2, 12 and 24;
 - Wrinkle Severity Rating Scale (WSRS), done by the blinded evaluating investigator at weeks 12 and 24;
 - o blinded evaluating investigator and subject satisfaction done at week 24;
 - o digital photography done before treatment and at weeks 2, 12 and 24.

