 - 12. Replace the used siringe in the box (without needle);
 - 13. Store in a safe place for future check.

Repeat the procedure for the LEFT side of the face.

Warnings: Do not use product after the expiry date. Do not use the product if the primary package is not intact or damaged. Do not use the product if it does not appear to be in normal condition. The siringes are disposable and CANNOT BE RESTERILISED; once the package has been opened, the material must be used immediately. Do not mix the medical devices with other substances. Do not place in contact the devices with quaternary ammonium salts as benzalkonium chloride. Do not inject any type of drug into the gel.

- Pain assessment. After implantation, participants will remain in a medical room for at least 60 minutes to be assessed for possible adverse events and for the pain. Pain will be assessed by the Blind Evaluator immediately (within 1 min) after the last injection and later after 15-30-45-60 min. by means of a 100-mm Visual Analogic Scale (VAS) (see paragraph 7), separately for each side.
- Adverse events will be monitored throughout the duration of the study (from obtainment of Informed consent to end of the study) and recorded in the subject's medical records and in the appropriate section of the CRF;
- An appointment will be taken for the next visit, scheduled after 2 weeks (\pm 2 days).

Visit 2 (week 2 ± 2 days): follow-up visit

The following assessments and procedures will be performed during Visit 2:

- All concomitant medications being taken by the subject will be checked and, in case of changes from the previous visit, will be recorded in the subject's medical records and in the appropriate section of the CRF;
- Vital signs (blood pressure and heart rate) will be measured and recorded;
- The occurrence of adverse events from the previous visit will be checked and (if any) and recorded in the subject's medical records and in the appropriate section of the CRF;
- The GAIS scale will be admnistered;
- The digital photo will be done;
- An appointment will be taken for the next visit, scheduled after 12 weeks from Visit 1.

Visit 3 (week 12 ± 10 days): follow-up visit

The following assessments and procedures will be performed during Visit 3:

- All concomitant medications being taken by the subject will be checked and, in case of changes from the previous visit, will be recorded in the subject's medical records and in the appropriate section of the CRF;

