Six GAIS forms will be provided for each subject, attached but not included in the CRF.

Clinical efficacy: objective evaluation

The aesthetic results of the treatment will be evaluated by the blind investigator, separately for each site (right/left), by means of the Wrinkle Severity Rating Scale (WSRS)⁴³, based on five scores, done before the treatment and a the weeks 12 and 24:

grade	wrinkle	description
1	absent	no visible nasolabial fold; continuous skin line
2	mild	shallow but visible nasolabial fold with a slight indentation; minor facial feature; implant is expected to produce a slight improvement in appearance
3	moderate	moderately deep nasolabial fold; clear facial feature visible at normal appearance but not when stretched; excellent correction is expected from injectable implant
4	severe	very long and deep nasolabial fold; prominent facial feature; <2 mm visible fold when stretched; significant improvement is expected from injectable implant
5	extreme	extremely deep and long nasolabial fold, detrimental to facial appearance; 2–4 mm visible V-shaped fold when stretched; unlikely to have satisfactory correction with injectable implant alone

The WSRS score will be entered directly in the CRF by the blinded evaluator.

At the final visit both the blind investigator and the subject will express a global satisfaction assessment (GSA) on corrective procedure (for each side of the face):

Global satisfaction assessment	(GSA)) scale
--------------------------------	-------	---------

unsatisfying	satisfying	very satisfying
0	1	2

⁴³ Day DJ, Littler CM, Swift RW et al . *The Wrinkle Severity Rating Scale. A validation study*. Am J Clin Dermatol 2004; 5 (1):49-52

Clinical efficacy: objective recording

Immediately before treatment, after treatment (within 1 hour) and at all follow-up visits (V2-V3-V4) a digital picture of the face will be taken.

The photo will be taken from a frontal point of view according to the standard procedures of the study site (sitting position of the subject; soft environmental daylight; neutral uniform background; digital camera; distance subjects camera 1,2-2.0 m; focal lenght adjusted to 70-90 mm [35 mm format equivalent]; neutral white balance; automatic ISO exposure).

As soon as possible the digital file will be copied in a PC: for each photo almost the date of the shot and the subject number will must available. A separate backup of the files is advisable.

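### Local reactions that arise after the first hour and resolve before Visit 2 are liable to be under-recorded, which weakens the HAL versus HA safety comparison

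*Combined protocol and SAP*

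**What the plan says.** Section 2.2 makes safety a comparative objective: "To assess and compare the safety of HAL and of HA". Section 8 takes the incidence of local and systemic adverse events as the first safety endpoint, and section 10.2.5 compares treatment-emergent events between treatments by the McNemar test.

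Section 1.4 describes what to expect: "The most common adverse events are local pain, brusing, ecchimosys, erythema and bleeding - generally mild and transient". Section 1.2 adds that some studies of fillers with and without lidocaine found "less erythema, swelling, and bruising with adjunct lidocaine". Swelling is named there, not in the list of common events in 1.4.

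On collection, section 6.1 says that after injection "participants will remain in a medical room for at least 60 minutes to be assessed for possible adverse events". The next visit is Visit 2, at week 2 ± 2 days, where events since the previous visit are checked. Section 9.2 has the investigator collect events "derived by spontaneous, unsolicited reports of subjects, by observation and by routine open questionings". The schedule in section 6 shows no call, diary or checklist in between; the only diary mention, in 14.2.3, is generic. The adverse event details required by 9.4 include duration, intensity and relationship to the device, but not the side of the face. Section 9.1 does not count local pain or burning up to 3 hours after the procedure as an adverse event.

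On photographs, section 7 says: "Immediately before treatment, after treatment (within 1 hour) and at all follow-up visits (V2-V3-V4) a digital picture of the face will be taken". Section 2.2 lists "digital photography done before treatment and at weeks 2, 12 and 24". Section 6.1 lists one Visit 1 photograph, ahead of the treatment steps, and the schedule has a single Visit 1 entry.

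**The concern.** In a split-face trial the subject is the matched pair, and the McNemar test uses only subjects in whom an event is recorded on one side and not the other. A local event therefore informs the comparison only if it is recorded and assigned to the correct side.

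Bruising, ecchymosis, erythema and swelling are the local reactions for which the protocol gives some reason to expect a lidocaine effect, and 1.4 calls the common reactions mild and transient. One that appears at home and has faded by Visit 2 reaches the CRF only if the subject reports it or recalls it in answer to an open question, and its side, intensity and dates then rest on memory.

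At stake is the meaning of a null result. Section 1.2 already describes the two formulations as having the same safety profile apart from pain. Finding no difference could be read as confirming that when it partly reflects incomplete recording.

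**Working it through.** **The plan's own figure.** Section 10.2.1 gives 81% power for 52 subjects, mean paired difference 1.0, SD of differences 2.5, two-sided alpha 0.05. The noncentrality is (1.0/2.5) × √52 = 2.884 on 51 degrees of freedom, and the noncentral t distribution gives 80.8%. The figure reproduces, but it covers pain only. The documents state no power, event rate or detectable difference for the safety comparison.

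**How each outcome is collected.**

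| Outcome | Recording | By side? |
|---|---|---|
| Pain (7) | Ten VAS forms per subject, five times in the first hour | Yes |
| GAIS (7) | Six forms per subject, weeks 2, 12, 24 | Yes |
| WSRS (7) | Blinded evaluator, baseline, weeks 12 and 24 | Yes |
| Local reactions, first hour (6.1) | Observation, no fixed form described | Not stated |
| Local reactions, then to Visit 2 (6.1, 9.2) | Spontaneous report and open question | Not stated |

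**What incomplete recording does.** Let p_HA and p_HAL be the true proportions of subjects with a reaction on each side, p11 the proportion with both, and c the share recorded, equal on both sides.

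- Observed difference = c × (p_HA − p_HAL). With 60% v 30% and c = 0.5: 0.5 × 0.30 = 0.15.
- p11 = p_HA·p_HAL + ρ√[p_HA(1−p_HA)p_HAL(1−p_HAL)].
- If the sides are lost independently, the recorded discordant proportions are c·p_HA − c²·p11 and c·p_HAL − c²·p11. If a subject's record is lost as a whole, c² becomes c.

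Worked case, 60% v 30%, ρ = 0, so p11 = 0.18:

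- Full recording: 0.42 and 0.12, sum 0.54, or 52 × 0.54 = 28.1 discordant subjects; power 82%.
- c = 0.5, sides lost independently: 0.30 − 0.045 = 0.255 and 0.15 − 0.045 = 0.105, sum 0.36, or 18.7 subjects; power 36%.
- c = 0.5, subjects lost as a whole: 0.30 − 0.09 = 0.21 and 0.15 − 0.09 = 0.06, sum 0.27, or 14.0 subjects; power 47%.

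Power is that of the exact two-sided McNemar test at 0.05, averaged over the binomial number of discordant subjects out of 52. The ranges below cover ρ = 0 to 0.3 and both kinds of loss.

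| Assumed true rates, HA v HAL | c = 1 | c = 0.75 | c = 0.5 | c = 0.25 |
|---|---|---|---|---|
| 60% v 30% | 82–94% | 60–84% | 36–61% | 14–19% |
| 50% v 30% | 46–62% | 30–46% | 18–28% | about 7% |
| 40% v 20% | 52–68% | 36–52% | 21–31% | about 7% |

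The rates, ρ and c are all assumptions. The table shows the direction and sensitivity of the effect, not a forecast.

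**The case against.** The plan is not blind to these events. Subjects are watched for at least 60 minutes, adverse events are recorded from consent to study end, inclusion criterion 5 in 4.2 obliges subjects to report events throughout, and Visit 2 looks back to Visit 1. Bleeding and erythema may well appear under observation, and some bruises may last to Visit 2. Safety is a secondary comparison with no power claim, it also covers systemic and late events over 24 weeks, and open questioning is an accepted way to collect adverse events. All of this stands, and it limits the point to under-recording of one class of event.

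Several stronger readings are tempting but unsupported:

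- A reader might infer that the plan misses transient reactions altogether. The provisions above rule that out.
- A reader might divide 60 minutes by 14 days (20,160 minutes) and conclude that 0.3% of the risk period is observed. That treats every minute as equally risky, and the documents give no onset or resolution times.
- A reader might assume that discordant pairs fall in proportion to the share recorded. When the sides are lost independently they do not: the worked case gives 0.36/0.54 = 0.67 at half recording, because some two-sided reactions are recorded as one-sided.
- Section 1.4 says "Early adverse reactions to hyaluronic acid fillers include vascular infarction and compromise", and a reader might infer that such an event at home would be found only if the subject calls. At most that applies before Visit 2. The consent pages are not available, so what subjects are told about contacting the site cannot be judged.
- A reader might infer that side is lost. The CRF is not in the documents, and relationship to the device can imply side, since each device is on one side. What can be said is that the text does not require side to be recorded.
- A reader might infer that sites would not take the 1-hour photograph. Section 7 requires it, and one Visit 1 entry is compatible with two pictures. The passages leave it open to omission. A picture at one hour would in any case not cover the following two weeks.

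**Conclusion.** The point holds as a cheap improvement to a secondary objective; the primary pain endpoint is unaffected. Between the end of the observation stay and Visit 2 there is no scheduled contact and no solicited per-side record, so reactions that arise and resolve in that interval are liable to be under-recorded.

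The pull towards no difference depends on the loss being equal on the two sides; if it is unequal, the documents do not show which way the comparison would move. The size cannot be derived from the plan. The fall in power from 82–94% to 36–61% applies only to assumed rates of 60% and 30% with half of all reactions recorded. A finding of similar local safety under this scheme should be described as weak evidence.

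The photograph discrepancy between section 7 and sections 6.1 and 2.2 is a separate, minor inconsistency that needs reconciling in any case.

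**What to change.** 1. Add a fixed right/left checklist of bruising/ecchymosis, erythema, bleeding and swelling (present or absent, intensity), completed by the Blinded Evaluator at the end of the 60-minute stay and at Visit 2. Leave out local pain and burning within 3 hours, which 9.1 excludes as an adverse event and the VAS measures in the first hour.
2. Give each subject a one-page right/left card for days 1–14 listing the same reactions, collected at Visit 2. Add side of face to the details required for each local adverse event in 9.4.
3. Reconcile the photograph within 1 hour after treatment across section 7, section 6.1, the schedule and section 2.2.
4. Keep open questioning for all other adverse events, and report solicited and spontaneous events separately.

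The cost is one CRF page and one card, with no extra visit. The evaluator is already present in the first hour for the VAS; section 6.1 does not say who conducts Visit 2, so the evaluator's attendance there should be stated. The downside is higher absolute counts of mild reactions, which separate reporting makes visible.
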